4.4 Multiplicity

No multiplicity adjustments will be made to any alpha levels used for statistical testing for efficacy endpoints. P-values < 0.05 at the interim analysis were used as an indication of treatment effect for all efficacy endpoints. P-values for all subsequent analyses performed are considered nominal, without conclusions drawn about statistical significance levels.

4.5 Analysis Populations

The following analysis populations will be defined.

Safety Population: The Safety population will be defined as all subjects who receive IP. Safety endpoints for subjects will be summarized and analyzed according to the treatment actually received. All safety analyses will be based on the Safety population.

Intent-to-Treat (ITT) Population: The ITT population will be defined as all subjects who are randomized. Subjects will be summarized and analyzed in the treatment group to which they are randomized. The analysis of the primary and secondary efficacy endpoints (mid-level PUL 1.2) will be based on the ITT population.

Modified Intent-to-Treat (mITT) Population: For each efficacy parameter, the mITT population included subjects in the ITT population who had at least a baseline observation (i.e., mITT populations are parameter-specific). Subjects were summarized and analyzed in the treatment group to which they were randomized. At the interim analysis, the primary and secondary efficacy (mid-level PUL 1.2) parameter analyses were repeated using the mITT population as

a supportive analysis. It was found that the mITT Population is equivalent to the ITT Population, so the mITT population was not considered for subsequent analyses and will not be considered for the final analysis.

Per Protocol (PP) Population: The PP population will include subjects who receive IP with no protocol deviations/violations that could significantly impact the completeness, accuracy and/or reliability of the trial data. The list of subjects in the per protocol population will be compiled prior to database lock. The primary, secondary and exploratory efficacy endpoint analyses will be evaluated using the PP population.

A summary of the number and percentage of subjects in each analysis population will be provided. For the mITT population, the number and percentage will be based on the primary efficacy endpoint. A listing of subject assignment into each analysis population will also be displayed.

5 STUDY POPULATION PARAMETERS

The study population parameters to be listed and summarized are described below. The ITT population will be used for the listings and summaries. Some of the summaries may also be done for other analysis populations defined in Section 4.5. All summaries will be presented by treatment group.

5.1 Eligibility and Informed Consent

Eligibility and informed consent parameters will be listed and will include date of informed consent/assent, consent to the collection and storage of exploratory biomarkers, participation in HOPE-1 protocol, protocol version, inclusion and/or exclusion criteria that were not met, if applicable, randomization date, and PUL 1.2 entry item score at randomization.

The number of subjects meeting all screening eligibility criteria and reasons for screen failure will be summarized.

5.2 Protocol Deviations

Protocol deviations will be listed and may include, but are not limited to:

- Visit not done or out-of-window
- Assessment not completed or out-of-window
- Inclusion/Exclusion
- Informed Consent/Assent
- IP Administration

The number and percentage of subjects with a protocol deviation will be summarized by protocol deviation category.

5.3 Demographics and Baseline Characteristics

Demographic and baseline characteristics will be listed and summarized. Demographic characteristics consist of age, sex, ethnicity, and race. A subject's age in years is calculated using the date of the informed consent/assent and date of birth using the following formula:

$$\text{Age} = [(\text{Informed Consent/Assent Date} - \text{Birth Date} + 1)/365.25].$$

Based on age, patients will be categorized as either pediatric (age ≤ 16) or adult (age > 16).

Baseline characteristics to be summarized include ulna length, height, weight, body mass index (BMI), screening PUL 1.2 entry item score, screening PUL 1.2 entry item score binary stratification (2, 3 vs. 4, 5) and dystrophin mutation type. In addition, subjects using a wheelchair or scooter for part-time and for full-time will be summarized. Subject height is either measured (i.e., standing height) or calculated from the subject's ulna length.

5.4 Medical Status Questionnaire

Subject medical status will be displayed in subject listings, which will include date of completion, frequency of walker and manual/power wheelchair or scooter use, ventilatory support, supplemental oxygen use, and frequency of falls in the last 30 days.

5.5 General Medical History

General medical history will be coded using Medical Dictionary for Regulatory Activities (MedDRA) version 21.0. Medical history will be listed and summarized. The summary will be presented by MedDRA System Organ Class (SOC) and Preferred Term (PT). At each level of subject summarization, a subject will be counted only once if that subject experienced the event more than once.

5.6 DMD Medical History

The following DMD medical history will be listed and summarized:

- Age at diagnosis (years),
- Age at first chronic glucocorticoid (years),
- Loss of stair climb and age at loss of stair climb (years),
- Loss of stair descend and age at loss of stair descend (years),
- Use of a walker and age at first walker use (years),
- Part-time use of a manual/power wheelchair or scooter and age at first part-time use of a manual/power wheelchair or scooter (years),
- Transition to full-time use of a manual/power wheelchair or scooter and age at first full-time use of a manual/power wheelchair or scooter (years),
- Start of non-invasive ventilatory support and age non-invasive ventilatory support started (years),

- Use of a mechanical cough assist device and age at first mechanical cough assist device use (years),
- History of spine surgery,
- History of symptomatic heart failure and age at first symptoms of heart failure (years), and
- History of medical (non-surgical) hospitalizations.

The following genetic testing results included in the DMD medical history will be listed:

- Date genetic testing sample collected
- Name of testing lab (if Clinical Laboratory Improvement Amendments (CLIA) certified)
- Mutation type
- Exon

5.7 Donor-Specific Antibodies

Donor, donor profiles, allele, HLA, HLA Class and MFI will be listed by subject and visit. Subject HLA profiles will be provided in a separate listing.

DSA data will be analyzed in the context of immune sensitization syndrome should there be an occurrence.

5.8 Physical Examination

All physical examination results will be listed. A shift table will be presented by body system for physical examination findings.

5.9 Prior and Concomitant Medications

Prescription, over-the-counter, and alternative medication use will be coded to drug class, preferred drug name, and generic/trade drug name using the World Health Organization Drug Global dictionary (WHODrug Global) version September 1, 2017. Medications that were stopped before the start of the IP administration procedure will be considered “pre-treatment.” All other medications will be considered “concomitant.” Medications that were started or ongoing at the time the IP administration procedure was started will be considered “baseline” (a subset of “concomitant”). Pre-treatment, baseline, and concomitant medications will be listed separately.

Frequencies and percentages of subjects reporting or receiving cardiac and steroid medications will be summarized by WHODrug Global Anatomic Therapeutic Chemical (ATC) Level 2 and Preferred Term. Pre-treatment and baseline cardiac and steroid medications will be summarized separately from concomitant cardiac and steroid medications.

At each level of subject summarization, subjects who reported one or more medication within that level are only counted once for that level.

5.10 Planned Medical/Surgical Procedures

All reported elective medical and/or surgical procedures (e.g., wisdom tooth extraction) that were not the result of an adverse event will be displayed in subject listings. For each procedure, the type of procedure, indication, and start/end date will be reported.

Any administered medication(s) related to the planned medical/surgical procedure(s) will be captured as a concomitant medication.

5.11 IP Administration

Details of IP administration will be listed. The number of subjects that completed IP infusion at each visit will be summarized. This is defined as subjects that completed (without interruption or syringe pump interrupted and restarted) both IP syringe administrations. For each visit, the total dose delivered (M cells) from both the first and second IP syringe administration, the number of patients who completed each IP syringe administration, reasons IP syringe was not completed, duration of IP administration (minutes), and total dose of IP syringe delivered (M cells) will be summarized. In addition, for the second IP syringe, the reasons the second IP syringe was not administered will also be summarized.

5.12 Subject Study Progress

A listing of subject study progress will show dates of per protocol study visits and unscheduled visits. The number of subjects who completed each visit will be summarized.

5.13 Subject Disposition

All screen failures will be listed along with the primary reason for screen failure.

Subject disposition will be summarized by treatment group for the ITT population overall, by site, and by the binary stratification of entry item score of PUL 1.2 at screening. The number of subjects who completed the study, the number of subjects who discontinued from the study, and the primary reason for discontinuation will be summarized.

6 EFFICACY ANALYSES

Listings and summaries of the efficacy parameters will be done for the ITT population, unless indicated otherwise. All summaries will be presented by treatment group. Efficacy parameters are described below.

6.1 Primary Efficacy Endpoint

The primary efficacy endpoint is change from baseline to Month 12 in the mid-level (elbow) dimension of the PUL 1.2. The hypothesis set to be tested is:

$$H_0: \mu_c - \mu_p = 0$$

$$H_a: \mu_c - \mu_p \neq 0$$

where μ_c and μ_p are population mean absolute changes from baseline in CAP-1002- and placebo-treated patients, respectively.

A MMRM analysis will be used to analyze the primary efficacy endpoint using the ITT population. The results for Month 3, 6, 9 and 12 visits will be modeled with visit, treatment, and treatment-by-visit interaction as the main effects; baseline measurement, site and binary stratification of entry item score of the PUL 1.2 at screening (2, 3 vs. 4, 5) will be included as covariates in the model. An autoregressive (AR(1)) covariance structure will be the covariance structure to model within-subject errors. The Kenward-Roger's (K-R) approximation will be used to estimate the denominator degrees of freedom. The primary comparison will be the contrast between CAP-1002 and placebo at Month 12.

As a supportive analysis, the analysis may be evaluated in the PP population.

6.2 Secondary Efficacy Endpoints

Supportive secondary efficacy endpoints will be change from baseline in:

- Mid-level (elbow) dimension of the PUL 1.2 at Months 3, 6, and 9;
- Regional systolic LV wall thickening at Months 6 and 12.

For both secondary efficacy endpoints, the same model described in Section 6.1 will be used. For the mid-level (elbow) PUL 1.2 analysis, the comparisons of interest will be the contrasts between CAP-1002 and placebo at Months 3, 6, and 9. For the regional systolic LV wall thickening analysis, the comparisons of interest will be the contrasts between CAP-1002 and placebo at Months 6 and 12.

As supportive analyses, these analyses may be evaluated in the PP population.

6.3 Exploratory Efficacy Endpoints

For an exploratory analysis, the mean change from baseline for the endpoints defined below will be analyzed using the same model described in Section 6.1.

As supportive analyses, these analyses may be evaluated in the PP population.

6.3.1 PUL Scale

All subjects, regardless of ambulatory status, will complete testing in both the 1.2 and 2.0 modules in the same preferred arm. All observed values will be listed. Observed totals and changes from baseline for each dimension [high-level (shoulder), mid-level (elbow), distal-level (wrist and hand)] will also be listed.

Using the model defined in Section 6.1, the comparisons of interest will be the contrasts between CAP-1002 and placebo for change from baseline in the following:

- Combined mid-level (elbow) and distal-level (hand and wrist) dimensions of the PUL 1.2 at Months 3, 6, 9, and 12;
- Combined high-level (shoulder), mid-level (elbow) and distal-level (hand and wrist) dimensions of the PUL 1.2 at Months 3, 6, 9, and 12;
- Mid-level (elbow) dimension of the PUL 2.0 at Months 3, 6, 9, and 12;
- Combined mid-level (elbow) and distal-level (hand and wrist) dimensions of the PUL 2.0 at Months 3, 6, 9, and 12;

- Combined high-level (shoulder), mid-level (elbow) and distal-level (hand and wrist) dimensions of the PUL 2.0 at Months 3, 6, 9, and 12.

6.3.2 Strength Testing

All subjects, regardless of ambulatory status, will complete grip, pinch (tip and key), and elbow flexion strength testing on the same side throughout the duration of the trial. Absolute values will be measured and their corresponding changes from baseline will be listed and summarized.

Using the model defined in Section 6.1, the comparisons of interest will be the contrasts between CAP-1002 and placebo for change from baseline in the following:

- Grip strength at Months 3, 6, 9, and 12;
- Tip-to-tip pinch strength at Months 3, 6, 9, and 12;
- Key pinch strength at Months 3, 6, 9, and 12;
- Elbow flexion strength at Months 3, 6, 9, and 12.

6.3.3 DMD Upper Limb PROM

The subject or parent/caretaker will evaluate the perceived difficulty in performing the activities of daily living classified into four domains including Food/Nutrition, Self Care, Household/Environment, and Leisure and Communication. Observed values and changes from baseline, overall and for each domain separately, will be listed and summarized.

Using the model defined in Section 6.1, the comparisons of interest will be the contrasts between CAP-1002 and placebo at Months 3, 6, 9, and 12 for change from baseline in each domain and overall total score.

6.3.4 Pediatric Outcomes Data Collection Instrument

Subjects and parent/caretaker will complete the PODCI questionnaires independently of one another. Observed values for each of the 6 scales (Upper Extremity and Physical Function, Transfer and Basic Mobility, Sports and Physical Functioning, Pain/Comfort, Happiness and Global Function) will be listed.

6.3.5 DMD Lifetime Mobility Scale

The subject and parents/caretakers will complete the DMD-LMS questionnaires independently of one another. Observed values for each of the 3 sub-domains (Walking and Moving, Changing and Maintaining Body Positions, Moving and Handling Objects) will be listed separately for subject-reported and parent/caretaker-reported values.

Using the model defined in Section 6.1, the comparisons of interest will be the contrasts between CAP-1002 and placebo at Months 3, 6, 9, and 12. The variable of interest is the change from baseline in the total score of a domain, calculated by summing selected items from the respective domain:

- Changing and Maintaining Body Positions Domain – Items 1, 2, 3, 6, 7, 8, 10, 13, 16, 17, 20, 22, 23, 24, 27

- Moving and Handling Objects Domain – Items 1, 2, 3, 4, 5, 7, 10, 11, 12, 13, 14, 15, 16, 17, 18, 19, 20, 22, 25, 28, 29, 31, 33, 36, 39, 42, 45, 47

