11.8.2. DMD Lifetime Mobility Scale

The Duchenne Muscular Dystrophy Lifetime Mobility Scale (DMD-LMS) is comprised of three sub-domains: 1) walking and moving, 2) transfers and trunk stability, and 3) carrying, moving, and handling objects. Each subdomain is scored out of 100 points. The questionnaire, completed separately by both the trial subject and parent/caretaker, facilitates patient-reported outcomes of function that can be combined with clinically-relative milestones specific to patients with DMD.

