14.5.3. Exploratory Efficacy Endpoints

Exploratory efficacy endpoints will be change from baseline in:

- High-level (shoulder) dimension of the PUL 1.2 at Months 3, 6, 9, and 12;
- High-level (shoulder) dimensions of the PUL 2.0 at Months 3, 6, 9, and 12;
- Mid-level (elbow) dimensions of the PUL 2.0 at Months 3, 6, 9, and 12;
- Distal-level (wrist and hand) dimensions of the PUL 1.2 at Months 3, 6, 9, and 12;
- Distal-level (wrist and hand) dimensions of the PUL 2.0 at Months 3, 6, 9, and 12;
- Grip strength, absolute and percent predicted, at Months 3, 6, 9, and 12;
- Tip-to-tip pinch strength, absolute and percent predicted at Months 3, 6, 9, and 12;
- Key pinch strength, absolute and percent predicted at Months 3, 6, 9, and 12;
- Elbow flexion strength, absolute and percent predicted, at Months 3, 6, 9, and 12;
- DMD UL-PROM at Months 3, 6, 9, and 12;

- PODCI scales (subject and parent) at Months 3, 6, 9, and 12;
- DMD-LMS at Months 3, 6, 9, and 12;
- NSAA at Months 3, 6, 9, and 12;
- 10MWRT at Months 3, 6, 9, and 12;
- Incidence of loss of ambulation (10MWRT > 30 seconds) at Months 3, 6, 9, and 12;
- Pulmonary function tests (absolute and percent predicted [if available]) at Months 3, 6, 9, and 12;
- LV structure and function as assessed by cardiac MRI at Months 6 and 12;
- Biomarkers, which may include osteopontin, IL-1 β , IL-2, IL-6, IL-10, TNF- α , CXCL10, troponin I (cardiac, fast skeletal, slow skeletal), troponin T, CK-MM, CK-MB, creatine kinase (total), creatine phosphate, creatinine, myostatin, and follistatin at Months 3, 6, 9, and 12;
- Resource utilization, including hospitalizations for orthopedic injury or surgery and for pulmonary infections, over the course of the trial.

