8 DEVIATIONS FROM STATISTICAL METHODS IN THE PROTOCOL

This final version 3.0 of the statistical analysis plan (SAP) supersedes all previous versions.

There were no changes to the conduct of the study since the last protocol amendment. Analyses planned but not performed and the rationales for the changes are as follows.

The following exploratory efficacy endpoints will not be analyzed:

- High-level (shoulder) dimension of the PUL 1.2;
- Distal-level (wrist and hand) dimension of the PUL 1.2;
- High-level (shoulder) dimension of the PUL 2.0;
- Distal-level (wrist and hand) dimension of the PUL 2.0;
- Grip strength, percent predicted, at Months 3, 6, 9, and 12;
- Tip-to-tip pinch strength, percent predicted, at Months 3, 6, 9, and 12;
- Key pinch strength, percent predicted, at Months 3, 6, 9, and 12;
- Elbow flexion strength, percent predicted, at Months 3, 6, 9, and 12;
- PODCI scales (subject and parent) at Months 3, 6, 9, and 12;
- Parent/caretaker-reported DMD-LMS at Months 3, 6, 9, and 12;
- NSAA at Months 3, 6, 9, and 12;
- 10MWRT at Months 3, 6, 9, and 12;
- Incidence of loss of ambulation (10MWRT > 30 seconds) at Months 3, 6, 9, and 12;
- Biomarkers at Months 3, 6, 9, and 12;
- Resource utilization, including hospitalizations for orthopedic injury or surgery and for pulmonary infections, over the course of the trial.

Originally, it was planned to perform a supportive analysis of the primary efficacy endpoint on the mITT Population. However, it was discovered that the mITT Population is equivalent to the ITT Population, so analyses of efficacy will only be performed on the ITT and PP populations.

Also, originally, it was planned to perform the secondary and exploratory efficacy endpoint analyses on the PP population only. However, it was decided that the same model will be used for the secondary and exploratory endpoints as in the primary efficacy endpoint, so the analyses will be done on the ITT Population as well for all efficacy endpoints except DMD-LMS.

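### SAP 6.3.5 scores DMD-LMS from an unexplained, undeclared subset of items in two of three domains, and SAP 8 makes it the only efficacy endpoint not extended to ITT

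*SAP*

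**What the plan says.** **Protocol.** Section 11.8.2 divides DMD-LMS into three sub-domains and says: "Each subdomain is scored out of 100 points". Section 14.5.3 lists the endpoint as change from baseline in "DMD-LMS at Months 3, 6, 9, and 12", with no item subset and no restriction to particular sub-domains. Section 14.5 assigns secondary and exploratory efficacy endpoints to the PP population.

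**SAP scoring.** Section 6.3.5 provides that "Observed values for each of the 3 sub-domains (Walking and Moving, Changing and Maintaining Body Positions, Moving and Handling Objects) will be listed separately". It then applies the Section 6.1 model to a domain total "calculated by summing selected items from the respective domain". Two item lists follow. For Changing and Maintaining Body Positions the list is "Items 1, 2, 3, 6, 7, 8, 10, 13, 16, 17, 20, 22, 23, 24, 27". The other begins "Moving and Handling Objects Domain – Items 1, 2, 3, 4, 5, 7, 10, 11, 12, 13" and runs on to item 47. There is no list and no model contrast for Walking and Moving.

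**SAP population.** Section 6 makes ITT the default for efficacy summaries. Section 6.3 applies the Section 6.1 model, which is specified for ITT, to the exploratory endpoints and treats PP as an optional supportive analysis. Section 8 says that "the analyses will be done on the ITT Population as well for all efficacy endpoints except DMD-LMS".

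**SAP declaration of changes.** Section 8 sets out to list planned analyses that were not performed, with reasons. On DMD-LMS it names only the parent/caretaker version and the ITT exception. SAP Addendum 2.6 brings back the parent/caretaker version as a listing and leaves the scoring unchanged.

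**The concern.** DMD-LMS is a patient-reported measure, and quality of life is part of the trial's secondary objective. Three analytic choices (which items, which domains, which population) differ from the Protocol's description of the scale or from the treatment of every other efficacy endpoint analysed, and none carries a reason. With 20 randomised subjects, any of the three could change the direction or size of an estimated difference.

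SAP v3.0 was finalised after four interim analyses. SAP 3.3.2 to 3.3.4 describe the three later ones as using unblinded data, and Protocol 9.5 says designated sponsor personnel became unblinded after the first. A reader given only the item-subset result cannot tell whether the selection was fixed in advance or made with results in view.

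There is a practical problem too. Because the SAP sections disagree, a programmer cannot tell from the text whether the DMD-LMS model is to be run in ITT, in PP or in both.

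**Working it through.** No sample size, power or alpha figure in the plan depends on this point, so there is no stated figure to reproduce. The check is a count of items and a comparison of sections.

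**1. Item counts (input: the lists in SAP 6.3.5).** The documents do not give the number of items per domain. Assume that numbering within each domain starts at 1 and is consecutive. The highest number listed is then a lower bound on the number of items.

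| Domain | Items used | Highest number | Not used, at least | Share not used, at least |
|---|---|---|---|---|
| Changing and Maintaining Body Positions | 15 | 27 | 27 − 15 = 12 | 12/27 = 44% |
| Moving and Handling Objects | 28 | 47 | 47 − 28 = 19 | 19/47 = 40% |
| Both | 43 | 27 + 47 = 74 | 12 + 19 = 31 | 31/74 = 42% |

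On that assumption at most 43/74 = 58% of the items in the two modelled domains enter the score, and fewer if either domain runs past its highest listed number. If some numbers in the gaps are not separately scored items, fewer were dropped than the table shows. The SAP's own description of the items as selected still implies that some were left out.

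**2. Domains.** The Protocol and the SAP each name three. The SAP models two. The domain names also differ: Protocol 11.8.2 has transfers and trunk stability where the SAP has Changing and Maintaining Body Positions.

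**3. Population.**

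| Section | Population for DMD-LMS |
|---|---|
| Protocol 14.5 | PP (all secondary and exploratory endpoints) |
| SAP 4.5 | PP definition covers exploratory endpoints; the ITT definition names only the primary and secondary mid-level PUL 1.2 |
| SAP 6 | ITT unless indicated otherwise |
| SAP 6.3 with 6.1 | ITT, with PP optional |
| SAP 6.3.5 | Refers to the 6.1 model; states no exception |
| SAP 8 | Not extended to ITT; the only such endpoint |

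SAP 6 allows exceptions, so Section 8 could be read as supplying one. But 6.3 and 6.3.5, where the model is specified, do not carry it, and no section gives a reason.

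**4. Comparison with the neighbouring measure.** SAP 6.3.3 models the DMD Upper Limb PROM in every domain and in total. The restriction to chosen items and domains is therefore not a general rule for patient-reported outcomes in this SAP.

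**5. Timing.** SAP 3.3 reports one interim analysis and three more, and SAP 8 says v3.0 replaces all earlier versions. Those versions are not among the documents, and the interim table lists in the SAP appendices are redacted. The order of item selection and unblinding therefore cannot be established in either direction.

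**The case against.** The strongest reply has four parts.

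- **Population.** PP was the Protocol's choice for exploratory endpoints, and ITT was the later addition. This stands. A reader might infer that keeping DMD-LMS in PP departs from the Protocol, or that the PP result is post hoc; Protocol 14.5 rules out both. What remains is an unexplained sole exception and a conflict between SAP sections.
- **Timing and motive.** A reader might infer that the items were chosen after unblinded results were seen, to favour the product. The documents do not support that. The list may have been carried over from a SAP version written before unblinding, and the text says only that items were selected. Equally, nothing supplied shows prespecification.
- **Scoring.** Protocol 11.8.2 does not say how items convert to 100 points or that every item counts, and 14.5.3 names no score. The differing domain names leave room for a different instrument version or scoring key. This stands too: it cannot be concluded that the SAP score is invalid or foreign to the instrument, only that it differs from the Protocol's description without explanation.
- **Impact.** The endpoint is one of many exploratory ones, and SAP 4.4 treats p-values after the first interim as nominal. All three sub-domains are still listed. Not modelling Walking and Moving also fits SAP 6.3.6, where the ambulatory measures are listed only. That is a plausible reason, but the SAP does not state it. These points limit the weight of the finding; they do not supply the missing source, date or declaration.

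**Conclusion.** The point holds as a gap in documentation and reporting. SAP 6.3.5 replaces three 100-point sub-domain scores with item-subset totals in two domains, gives no source, date or reason, and does not declare the change in Section 8. The ITT exception in Section 8 is unexplained and conflicts with Sections 6 and 6.3. The counts of 15 and 28 items used are exact. The minimum of 31 items not used rests on consecutive numbering within each domain.

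The effect on the estimated treatment difference cannot be computed, because the documents give no item-level or domain-level data. The consequences are confined to one exploratory patient-reported outcome with nominal p-values. The change is nevertheless worth making, because it removes the dependence of the reported result on unexplained choices of items, domains and population.

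**What to change.** 1. Model the Protocol's 100-point score for all three sub-domains in both ITT, as for every other efficacy endpoint analysed, and PP, as in Protocol 14.5. State the scoring key that converts items to the 100-point scale and map the Protocol's sub-domain names to the SAP's.
2. Report the item-subset analysis beside it, with the source and date of the item list and the reason for the selection. Label it post hoc unless an earlier SAP version shows that it was set before unblinding. This label concerns the item selection only and should not be attached to the PP population.
3. Declare the item subset and the unmodelled domain in SAP 8, with reasons.
4. Reconcile SAP 6, 6.3, 6.3.5 and 8 on the population, and align the population definitions in 4.5.

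The cost is re-scoring data already collected, a few extra exploratory tables and some text. More exploratory contrasts will be shown, but they remain nominal and the primary analysis does not change.
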